Dry mouth is a medically based condition that impairs many facets of patients' quality of life. Persistent dry mouth, resulting from diminished or low salivary flow, contributes to burning mucosa, dental caries, difficulty with chewing swallowing and digestion of food, and candidiasis overgrowth. Current treatments focus on palliative care to rehydrate the mouth primarily with water using of chipped ice, sipping water throughout the day, and applying moisturizing gels and liquids intraorally through the day. However, the effects of these treatments are temporary at best. There are more invasive and systemic treatments, but their use and effectiveness is limited, and may have unpleasant side effects. Medical devices have been employed to manage various systemic conditions in the last 15 years. Studies have demonstrated that the use of medical devices improve health outcomes due to mitigation of compliance and behavior modification issues, and therefore improvement in the health, and feeling of well beings in patients. The Voutia external oral irrigation device was designed to address the quality of patients' lives who suffer from dry mouth. Instead of patients carrying ice chips or water to use throughout the day, the device delivers continuous, hands-free water in adjustable flow levels. Early patient comments suggest an improvement in the quality-of-life issues associated with dry mouth. The aims of this study are to 1) assess patient perception of Oral Health Related Quality of Life (OHRQoL) using the Oral Health Impact Profile (OHIP-14) and the Xerostomia Inventory (XI), 2) assess salivary flow using salivary testing, and 3) mucosal appearances using the Clinical Oral Dryness Score (CODS) before and after the use of the Voutia device to deliver water intraorally for 4-6 weeks.

2. * Describe the study hypothesis and/or research questions. Use lay language whenever possible.

Medication and systemically-induced oral dryness can result in various conditions resulting in a severe reduction in quality of life. Current treatments given for diminished or no salivary flow are most often palliative and do not offer long term relief.

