Embarrassment because of problems with your teeth, mouth or dentures.

Irritability with other people because of problems with disability with your teeth, mouth or dentures.

Difficulty doing your usual jobs because of problems with your teeth, mouth or dentures.
 Feeling that life in general was less satisfying because of problems with your teeth, mouth or dentures.
 Inability to function because of problems with your teeth, mouth or dentures.

And clinically, alleviation of:

- 1) mirror sticks to buccal mucosa
- 2) mirror sticks to tongue
- 3) frothy saliva
- 4) no saliva pooling in floor of mouth
- 5) tongue shows loss of papillae
- 6) altered/smooth gingival architecture
- 7) glassy appearance of other oral mucosa, especially palate
- 8) tongue lobulated/fissured
- 9) active or recently restored (last 6 months) cervical caries (more than 2 teeth)
- 10) debris on palate (excluding under dentures)

6. * Describe any potential for direct social impact in this study . For example, any engagement with specific communities to respond to community-identified needs, or ways the study will strengthen the well-being of the specific communities if applicable:

Many different groups of people suffer from chronic dry mouth. This condition can be caused by medications, or health conditions, and can make it difficult to eat speak, and/or remain active. Standard treatment for dry mouth include using medications, rinses, and sipping liquids throughout the day. These treatments help some patients, but many patients still suffer silently with the discomfort of constant oral dryness.

The Voutia irrigation device is a non-surgical, external pump designed to pulse water into the mouth at a rate set by the patient . It is designed to help reduce the need for medications, rinses, and carrying and sipping beverages throughout the day, during meals, during exercise, and during sleeping times.

We want to use our clinical exam and survey to measure the effect of using the Votia device and learn if it will help people suffering from dry mouth to have an improvement in their quality of life, as well as in the health of their mouths.

7. Upload a supporting citation list if applicable:

ID: MS1_HM20021188

View: SF2 - Study Population

Study Population

1. * Provide the maximum number of individuals that

1. May participate in any study interaction or intervention (including screening, consenting, and study activities)

AND/OR

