2. Patients who are being treated at the VCU School of Dentistry in the pre-doctoral clinics will be recruited to participate based on their reporting xerostomia, or clinically demonstrating signs of xerostomia. Consent to be taken prior to Redcap survey completion.
2. PI or student dentists will ask the REdcap survey questions and collect the salivary testing for patients who report a dry mouth (xerostomia) and have consented to participate.

Saliva testing is done for all patients in our clinic who are suspected to have reduced salivary flow. It is not being done exclusively for this research. It is routinely performed and the instructions for the measuring of salivary flow is attached in documents as "Saliva Testing."

Flyers will be posted on walls in and around the dental school where our congregated, or wait. Elevators, halls, restrooms, operatories, door of the facility, bulletin boards, (email attached in documents.)

- When using email, it will be to patients determined by their treating dentist or student doctor to be suffering from dry mouth (xerostomia).
- Email addresses would be obtained through patient records, in the same manner that their phone numbers are taken from the patient records.
- As many necessary to obtain the final necessary number of patients for the study; estimate 50.
- We would send one email, with no follow up.

5. * Does this study have a separate protocol document (i.e. a multisite or sponsor's protocol) that contains a detailed description of the study's methodology?

- Yes
- No**

6. * Since a separate protocol document is not uploaded, describe the proposed research using language understandable to those IRB committee members whose expertise is not scientific. The description must include:

- 1. A statement explaining the study design**
- 2. A detailed description of all the procedures that will be followed to carry out the study, preferably in sequential order, and in sufficient detail that the study's methods could be replicated**
- 3. A description of all research measures/tests/interventions that will be used (if applicable)**

See the help text for additional guidance

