Patients who attend the dental clinic in the school of dentistry have medical and dental histories reviewed. An intraoral clinical exam is also performed to record intramural findings. Upon review by the PI of the recorded medical and dental histories, along with an intramural exam, if a patient has either reported xerostomia, or shows symptoms of salivary hypofunction, the patient will be asked if they would like to participate in the study. If the patient consents, consent will be obtained and the REDCap survey will be completed by the patient.

The patient will be instructed to wear the extra oral irrigation device continuously through the day and night, removing for cleaning and if otherwise necessary, but not for time extending beyond six-eight hours. Use and cleaning instructions to be given according to the manufacturers instructions (see attached Voutia Instruction guide).

After 4-6 weeks, the patient will be instructed to return to the dental school clinic for reexamination and completion of the survey.

7. * The IRB only reviews research activities, so indicate which of the study activities are:

- Being performed exclusively for research purposes (i.e. they would not otherwise be done apart from this study) **VERSUS.**

- Alterations of routine activities/procedures (e.g. the study is altering the timing, frequency, method, location, amount, etc.) **VERSUS.**

- Being done for other purposes and whose data/results will be used secondarily in the study (e.g. standard medical or psychological tests, routine education practices, quality improvement initiatives, etc.).

The wearing of the oral irrigation device and the completion of the survey are done exclusively for research purposes.

Standard dental exams will be completed for non-research purposes but data from these exam/interviews will be used for the study.

8. If applicable, describe alternatives (research or non-research) that are available to potential participants if they choose not to participate in this study:

Patients are routinely given, and will be given standard instructions for dry mouth if they choose to not participate.

These instructions include sipping water through the day, using salivary substitutes through the day, rinsing through the day with baking soda and water rinse, chewing or sucking on sugar-free gums and mints (in particular products containing Xylitol), and the use of 5000 ppm prescription strength fluoride preparations at home in place of OTC toothpaste.

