NCT04901507

Effects of an External Oral Irrigation Device on Patients With Dry Mouth

07/01/2021

Statistical Analysis Plan

The responses from the OHIP -14 and XI surveys are scored on a five-point scale (OHIP-14: 0-4, XI: 1-5). The examiner scores the features observed in the patient's mouth and derives a COD score of 0-10. Clinical findings observed are given a one-point value for CODS, with 10 indicating the most severe oral dryness.

Unstimulated salivary flow (USSF) will be tested prior to stimulated flow to enhance accuracy. USSF is measured using a Schirmer strip placed on the floor of the mouth with the patient seated upright. Next, the patient is given unflavored wax to chew and is instructed to expectorate into a medicine cup for three minutes to yield the stimulated salivary flow (SSF).

Scores will be compared before and after use of the device with paired t-tests, assuming data demonstrates normal distribution. If not, nonparametric alternatives will be utilized. SAS EG v.8.2 (SAS Institute, Cary, NC) will be used for all analyses. Significance level is set at 0.05.

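### CODS item 9 looks back six months but follow-up is 4-6 weeks, so it is very unlikely to register a device effect and can change for unrelated reasons; report the CODS change with and without it.

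*Protocol*

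**What the plan says.** - **Score.** The SAP states: "The examiner scores the features observed in the patient's mouth and derives a COD score of 0-10". It adds: "Clinical findings observed are given a one-point value for CODS, with 10 indicating the most severe oral dryness". Scores are compared with paired t-tests, or nonparametric alternatives if the data are not normal, at the 0.05 level.
- **Features.** Protocol, Background, Rationale and Goals, question 5 (direct benefits) introduces ten features with "And clinically, alleviation of". Item 9 is "active or recently restored (last 6 months) cervical caries (more than 2 teeth". The list is not labelled CODS, but ten features fit a score of 0-10 with one point each.
- **Timing.** Question 1 of the same section describes the comparison as "before and after the use of the Voutia device to deliver water intraorally for 4-6 weeks". Study Procedures, question 6, states: "After 4-6 weeks, the patient will be instructed to return to the dental school clinic for reexamination and completion of the survey". That is the only follow-up examination, and no comparator group is described.
- **Setting.** Study Procedures, question 4, states: "Patients who are being treated at the VCU School of Dentistry in the pre-doctoral clinics will be recruited to participate".
- **Not stated.** Neither document says how item 9 is rescored at follow-up, from which date the six months run, or whether the item enters the change score.

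**The concern.** The look-back of item 9 is several times longer than the interval between the two examinations. Its value at follow-up therefore depends largely on events before enrolment and on dental treatment, and hardly at all on what the device could do in 4-6 weeks. Followed as written, the SAP would count any change in the item as a change in CODS, and without a comparator nothing offsets it.

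The item matters in this population. The Protocol's background says dry mouth contributes to caries, and participants are under care in dental clinics, where caries is found and restored. CODS is the outcome for the third aim. The sample size section says the pilot should supply estimates for sizing a larger study, so unrelated movement would enter both the mean and the SD of change carried forward.

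**Working it through.** **Inputs from the documents.** Look-back 6 months; threshold more than 2 teeth, so at least 3; one point per item; follow-up w = 4 or 6 weeks; at most 25 patients. The plan gives no effect size, SD or power for CODS, so there is no figure of its own to reproduce.

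**Assumptions.** Restoration dates uniform over the look-back. Share q of patients who score item 9 only through past restorations: 10-50%. SD of change in the other items: 1.0-2.0 points. Two-sided test, since the SAP does not state sidedness.

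**Step 1: apply the scoring rule.**

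| Situation | Baseline | Follow-up |
|---|---|---|
| Caries active at both visits | 1 | 1 |
| Caries active at baseline, restored during the study | 1 | 1 |
| Scored through restorations only; ageing leaves 2 or fewer qualifying teeth | 1 | 0 |
| New caries brings the count to 3 or more teeth | 0 | 1 |
| Lesions judged no longer active, not restored, leaving 2 or fewer teeth | 1 | 0 |

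Only the last row could reflect a device effect.

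**Step 2: window.** 6 months = 6 × (365/12)/7 = 26.07 weeks, which is 26.07/6 = 4.3 to 26.07/4 = 6.5 times the follow-up. A restoration leaves the window between visits only if it was placed 22.1-26.1 weeks (w = 4) or 20.1-26.1 weeks (w = 6) before baseline.

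**Step 3: chance that a restoration-only patient loses the point by date.**
- All teeth restored at one visit: w/26.07, so 4/26.07 = 15.3% and 6/26.07 = 23.0%.
- Exactly 3 teeth on independent dates: 1 − (1 − w/26.07)³ = 39.3% and 54.4%.
- More teeth on independent dates (binomial chance that 2 or fewer remain): 4 teeth, 11.4% and 22.9%; 5 teeth, 2.8% and 8.4%.

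**Step 4: shift in mean CODS = q × that chance.**
- One visit: 0.10 × 0.153 = 0.015 to 0.50 × 0.230 = 0.115, or about 0.02-0.12 point. Among 25 patients this is 0.4 to 2.9 patients.
- Exactly 3 teeth on independent dates: 0.10 × 0.393 = 0.039 to 0.50 × 0.544 = 0.272 point.

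**Step 5: effect on the paired t-test.** Simulation, n = 25, 40,000 runs, no mean change in the other items, and only date-driven falls (no offsetting rises). Ranges run over SD 1.0-2.0.

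| Downward shift in mean | Two-sided rejection rate |
|---|---|
| 0 | 0.048-0.052 |
| 0.05 | 0.052-0.055 |
| 0.115 | 0.059-0.079 |
| 0.27 (extreme) | 0.098-0.206 |

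For scale, the mean change detectable with 80% power is about (1.96 + 0.84) × SD/√25 = 0.56 × SD, or 0.56-1.12 points.

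**Step 6: item 9 held at baseline.** Its contribution to every patient's change is then 0, exactly as if it were omitted. The date-driven shift disappears, and the rejection rate is that of the first row, 0.048-0.052.

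**The case against.** A reader might infer three stronger things, and the documents support none of them.

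- **That the item cannot show benefit.** It also counts active caries, so a lesion judged inactive at follow-up without restoration would clear it. The documents give no activity criteria and no evidence on whether this happens within 4-6 weeks. Very unlikely is as far as one can go.
- **That the score will show a false improvement.** Falls by date are possible, but new caries moves the item the other way. If teeth enter and leave the window at equal rates, the expected net change is zero.
- **That an insensitive item weakens the comparison by a tenth of the scale.** In a paired analysis, an item scored 1 at both visits adds nothing to the mean change or to its variance. Only patients whose item 9 changes matter.

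Other objections carry weight. The size rests wholly on assumed prevalence and dates, and the larger shifts need half the sample to be restoration-only positives with exactly three teeth restored on separate dates. This is a pilot that is not powered for tests. Scoring instructions may sit in uploaded forms that are not reproduced. Replacing the instrument's 0-10 total with a study-made 0-9 score as the main result would be a debatable trade. These points limit the size of the problem and the remedy. They do not remove the mismatch between look-back and follow-up, or the absence of a rescoring rule in the two documents.

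**Conclusion.** The concern stands in a limited form. Over 4-6 weeks item 9 is very unlikely to respond to the device, yet it can change by date or through new caries, and the SAP as written would count that movement in the before-after CODS change.

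Under the one-visit assumptions the date-driven part is about 0.02-0.12 point on a ten-point score, which raises the rejection rate to at most about 0.08. Larger distortion needs extreme assumptions, and new caries could offset or reverse the shift. The finding relies on reading the Protocol's ten features as the CODS items, which the matching count makes reasonable. It is a cheap improvement to the plan, not a flaw that undermines the study.

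**What to change.** **SAP.** Keep the 0-10 CODS change as planned. Add a pre-specified second analysis in which item 9 is carried at its baseline value at follow-up (numerically the same as omitting it from the change). Report both, and rest any claim of CODS improvement on agreement between the two.

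**Protocol, Background, Rationale and Goals, question 5.** Remove item 9 from the features the device may alleviate over 4-6 weeks.

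**Cost.** One or two sentences in the SAP, one line in the Protocol and one extra analysis. No new examinations are needed, but the ten item scores must be kept, not only the total. The adjusted change is not the standard ten-item change, which is why both are reported.

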2. You obtain any data/specimens about (regardless of identifiability)

at VCU and at other sites under the VCU IRB's oversight. See the help text for additional guidance.

25

2. If this is a multi-Center Project, what is the maximum anticipated number of subjects across all sites?

NA

3. * Provide justification for the sample size by explaining how you arrived at the expected number of participants and why this number is adequate for answering the research questions:

This is a pilot study so the goal is not to power any statistical tests. This sample size is based on the number of available devices and clinic feasibility. This sample size should provide sufficient estimates to calculate the sample size requirements for a larger study if the pilot study justifies.

4. * List the study inclusion criteria:

Patients who report a dry mouth (xerostomia) to be screened. The OHIP-14, CODS, and the XI will be completed for those patients, along with stimulated and resting salivary flow testing to determine extent of oral dryness. The patients who report xerostomia (dry mouth) and are diagnosed after testing with hypofunctioning salivary glands will be included.

These patients may experience salivary hypofunction due to any of the following conditions: medication-induced, Sjogren's or other connective tissue disorders, Diabetes Mellitus, smoking-induced, post radiation therapy, or glandular dissection.

The clinics used for patient recruitment during this study treat adults only, and so children will not included.

5. * List the study exclusion criteria:

Patient who after testing do not exhibit salivary hypofunction.

The clinics used for patient recruitment during this study treat adults only, and so children will not included.

6. * Will individuals with limited English proficiency be included in or excluded from this research?

- Included
- Excluded - safety concerns if participants are unable to communicate with the study team
- Excluded - instruments/measures only validated in English
- Excluded - no prospect of direct benefit to individual participants
- Excluded - minimal risk study**
- Excluded - lack of budget/resources for translation and interpretation [provide an explanation in next question]
- Excluded - other reason [provide an explanation in next question]

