1. * Has this human subjects protocol (not the grant application) already been reviewed by the funder of a sponsored project (e.g. a federal, state or non-profit funding sponsor)?

Yes

No

16. Upload any documents requested in the questions above:

ID: MS1_HM20021188

View: SF2 - HIPAA

HIPAA

HIPAA Privacy Board Requirements

For guidance, see <https://www.vcuhealth.org/our-story/who-we-are/compliance-services/compliance-services>

1. * Select the source of the Individually Identifiable Health Information. See help text for definitions.

- PHI associated with or derived from (i.e. obtained from or entered into) VCU Health medical records or VCU Dental Care records
- Research Health Information (RHI) created or received by a study and kept solely in study records (e.g. self reported or the result of research tests and not entered into health records)
- PHI associated with or derived from (i.e. obtained from or entered into) a non-VCU HIPAA covered entity's health records

2. * Summarize the types of health information that will be obtained or used in this research. Do not describe only the identifiers that you will collect or use during the study.

Patients medical and dental history, salivary flow rates, and surveys that measure oral dryness and effects on quality of life due to oral dryness will be obtained at the start and end of the study.

3. * Describe the source(s) of the protected health information (e.g. which clinical databases):

The dental school stores the medical and dental history electronically in Axiom; this is where the information will be obtained, in addition to reviews of this information completed at time of appointments.

4. * Does the PI certify that this study's access to and use of the protected health information is limited to the minimum amount necessary to be able to effectively conduct the research?

Yes No

5. * Select all pathways this research will employ to use or access PHI (selections will branch):

- De-Identified Data (none of the 18 identifiers are recorded or associated with the research data)
- Limited Data Set
- Waiver of Authorization
- Partial Waiver of Authorization (temporary waiver for recruitment purposes and/or waiver of some elements of Authorization)
- Signed Authorization Combined with Consent Form
- Signed Authorization as Stand-Alone Form

ID: MS1_HM20021188

View: SF2 - Partial Waiver of Authorization

Partial Waiver of Authorization

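### Low measured flow gates entry and the plan does not separate that reading from the flow baseline; nor can a single arm answer whether the device should replace palliative care

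*Protocol*

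**What the plan says.** **Entry.** Study Population, question 4, has patients who report dry mouth complete the OHIP-14, CODS and XI, "along with stimulated and resting salivary flow testing to determine extent of oral dryness". It then states: "The patients who report xerostomia (dry mouth) and are diagnosed after testing with hypofunctioning salivary glands will be included". The exclusion criterion in question 5 mirrors this: "Patient who after testing do not exhibit salivary hypofunction".

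**When flow is measured.** HIPAA, question 2, says that "salivary flow rates, and surveys that measure oral dryness and effects on quality of life due to oral dryness will be obtained at the start", with a second set at the close. Data Confidentiality and Storage, question 9, refers to two survey timepoints. Study Procedures, question 4, says "Saliva testing is done for all patients in our clinic who are suspected to have reduced salivary flow", and also that the investigator or student dentists will "collect the salivary testing for patients who report a dry mouth (xerostomia) and have consented to participate". Study Procedures, question 6, sets out the invitation: "if a patient has either reported xerostomia, or shows symptoms of salivary hypofunction, the patient will be asked if they would like to participate".

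**Analysis.** The SAP describes how unstimulated and stimulated flow are measured, then says: "Scores will be compared before and after use of the device with paired t-tests, assuming data demonstrates normal distribution". It sets a 0.05 level, offers nonparametric alternatives, and does not define the before value.

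**Comparative question.** Background question 2 and Study Procedures question 1 ask whether using the device in place of current palliative treatments improves quality of life. Study Population, question 7, calls the device an additional treatment. The documents describe one treated group. They do not say whether participants stop, continue or record palliative measures.

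**The concern.** A single flow reading is partly stable and partly chance. Patients admitted because a reading was low include some who were low by chance that day, and on retest their flow tends to rise. If the same reading is also the baseline, that rise counts as change over the treatment period. A paired test without a control group cannot distinguish it from a device effect.

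The flow comparison (aim 2) is therefore at risk. The nominal error rate would not hold for a flow that gates entry. The estimated change would be too large, and a later trial sized on it would be too small.

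The comparative question is a separate matter. A before-after change in one group describes what happened during device use. It does not show what would have happened under palliative care.

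**Working it through.** **Is there a separate baseline?** The text places flow testing at screening, in consented patients, and at the start and end of the study. It nowhere says that these are different readings before device use. The test in consented patients might be a second reading or might be the selecting test itself: it is given to patients reporting dry mouth, alongside the same surveys. The Saliva Testing attachment could settle this, but it is listed without its content.

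**The plan's own figure.** The sample size of 25 rests on device availability and clinic feasibility, so there is no calculation to reproduce.

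**Inputs.** From the documents: at most 25 patients, a paired t-test, level 0.05. Assumed, because the documents do not give them: a two-sided test (hence 2.5% in the direction of improvement), normally distributed flow, retest correlation r, share of tested patients admitted p, no true change, and selecting reading = baseline.

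**Hand check, one flow gated by its own test.** The expected apparent gain, in SD of the tested population, is (1 − r) × φ(a)/p, with a the normal quantile of p. For p = 0.5 and r = 0.7:

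- Gain: 0.3 × 0.399/0.5 = 0.24.
- Variance of the selected first reading: 1 − 0.798² = 0.363.
- SD of the change: √(0.3² × 0.363 + 1 − 0.7²) = 0.737.
- Standardised change: 0.239/0.737 = 0.325.

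With 25 pairs this is 0.325 × 5 = 1.6 standard errors. The simulated chance of a significant gain is 34%.

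**Main case, two-test gate.** Both flows are tested, so the gate is taken as both low or either low. True flows are assumed to correlate 0.5, with independent measurement noise (20,000 simulated trials per cell). The false-gain rate per flow is:

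| Share admitted | r = 0.6 | r = 0.7 | r = 0.8 | r = 0.9 |
|---|---|---|---|---|
| 50% | 16%-18% | 13%-14% | 10% | 7% |
| 70% | 9% | 8% | 6% | 5% |
| 90% | 4% | 4% | 4% | 3% |

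For r from 0.8 down to 0.6, the spurious gain is 0.09-0.18 SD at 50% admitted, about 0.05-0.11 at 70% and 0.02-0.05 at 90%. The standard error of the mean change without selection is √(2(1 − r)/25), which is 0.126 at r = 0.8 and 0.179 at r = 0.6. At 90% admitted the bias is therefore about a quarter of a standard error at most (0.045/0.179 = 0.25).

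**Sensitivity, r = 0.6 to 0.8, at 50%, 70% and 90% admitted:**

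- Noise correlation 0.5 between the two flows: 17%-32%, 9%-15%, 4%-5%.
- One flow gated by its own single test: 24%-45%, 12%-20%, 5%-6%.
- The cap of 25 counts those screened (n about 12, 17, 22): 7%-10%, 5%-7%, 4%.
- Signed-rank test instead of the t-test: 10%-16%, 6%-9%, 4%. The SAP's fallback does not help.
- Same-day repeat as baseline, with half the noise at day level: 5%-7%, 4%-5%, 3%.
- Different-day baseline not used for selection: 2.3%-2.6% throughout.

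**Comparative question.** No arithmetic is needed. Answering it requires outcomes under palliative care without the device, and the plan collects none.

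**The case against.** The strongest reply is that the documents establish an undefined baseline, not a biased one. This stands. A reader might infer that the selecting reading is the baseline. The two time points make that the natural reading, but the text does not say it, and the attachment might say otherwise.

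Other limits also stand:

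- The SAP's comparison sentence speaks of scores, and flow is never called a score. That the paired test covers flow is inferred from the aims.
- A reader might take the protocol's stated wish to determine significance as a promise about flow. The sentence just before it concerns quality of life.
- The statement that the pilot will supply estimates for a larger study names no endpoint, so sizing on flow is a possible use rather than a stated one.
- A reader might see a contradiction between the flow criterion and the recruitment text. One says who is included and the other who is asked, so they can be successive steps. The sequence still needs clarifying.
- Patients are already selected for dryness, so a high share admitted, and hence a small bias, is plausible.

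On the comparative question, the aims and SAP claim only a before-after change, and no comparative conclusion is written down. The question itself is nevertheless framed as replacement, and the design cannot answer it.

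Pilot status removes the need for power. It does not make a change from a selected baseline attributable to the device.

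**Conclusion.** The point holds conditionally for flow and without numerical assumptions for the comparative question.

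For flow, if the selecting reading is the baseline and the paired test covers flow, a gain is expected with no device effect. Under the two-test gate with independent noise and retest correlation 0.6 to 0.9, the false-gain rate per flow is about 7%-18%, 5%-9% and 3%-4% at 50%, 70% and 90% admitted, against 2.5%. Cut-off, retest correlation, share admitted and noise structure are all assumed, so these figures show a possible range and do not estimate this trial's error rate. The higher figures for a single-test gate are not the expected case, because the protocol names both flow tests.

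A reader might extend the argument to the OHIP-14, XI and CODS. The documents do not support this calculation for them, since no score threshold for entry is stated.

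For the comparative question, the design supports a statement about change during device use and nothing about the device in place of palliative care.

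**What to change.** 1. **Flow baseline.** State in the SAP which reading is the baseline for unstimulated and stimulated flow, and whether the paired test covers flow. If the Saliva Testing attachment settles the baseline, cite it.
   - If every participant has a pre-device reading from a different day that was not used for eligibility, use it for all.
   - Otherwise keep one baseline definition for everyone and report the flow change descriptively. State that it is not attributable to the device and is not to be used uncorrected to size a larger study. Mixing baseline types in one paired test would need an analysis rule that the SAP does not have.
2. **Recruitment sequence.** Clarify how the flow criterion in Study Population fits the order of invitation, consent and testing in Study Procedures.
3. **Research question.** In Background question 2 and Study Procedures question 1, and in any conclusion, ask about change in quality of life over 4-6 weeks of device use and drop the replacement wording. Reconcile this with the description of the device as additional in Study Population, question 7.

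The cost is a few sentences in the SAP and a wording change in the protocol, with no added arm or visit. The downside is a more modest claim on flow and no claim against usual palliative measures.
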